3.3 Inclusion of Women and Minorities

Both men and women of all races and ethnic groups are eligible for this trial. Every attempt will be made to enter all eligible participants into this protocol in this rare set of diseases.

4. REGISTRATION PROCEDURES

4.1 General Guidelines for DF/HCC Institutions

Institutions will register eligible participants in the Clinical Trials Management System (CTMS) OnCore. Registrations must occur prior to the initiation of protocol therapy. Any participant not registered to the protocol before protocol therapy begins will be considered ineligible and registration will be denied.

An investigator will confirm eligibility criteria and a member of the study team will complete the protocol-specific eligibility checklist.

Following registration, participants may begin protocol therapy. Issues that would cause treatment delays should be discussed with the Overall PI. If a participant does not receive protocol therapy following registration, the participant's registration on the study must be canceled. Registration cancellations must be made in OnCore as soon as possible.

4.2 Registration Process for DF/HCC Institutions

DF/HCC Standard Operating Procedure for Human Subject Research Titled *Subject Protocol Registration* (SOP #: REGIST-101) must be followed.

5. TREATMENT PLAN

5.1 Treatment Regimen

This is a non-randomized phase 2 study of eribulin in combination with pembrolizumab for the treatment of liposarcomas, leiomyosarcoma, and undifferentiated pleomorphic sarcomas. Eligible participants with liposarcoma, leiomyosarcoma, or undifferentiated pleomorphic sarcoma/other sarcomas will be divided into three separate cohorts by histologic subtype. Arm A: Leiomyosarcoma, Arm B: Liposarcoma, and Arm C: Undifferentiated Pleomorphic Sarcoma/other sarcomas. A treatment cycle will be defined as 21 consecutive days. Treatment will be eribulin 1.4 mg/m² administered on Day 1 and on Day 8 of each 21-day cycle, plus pembrolizumab 200mg administered on Day 1, of each 21-day cycle. If treatment is delayed, protocol required restaging assessments will remain on-schedule. Eribulin and pembrolizumab will be administered on an outpatient basis. Reportable adverse events and potential risks are described in Section 7. Appropriate dose modifications are described in Section 6. No investigational or commercial agents or therapies other than those described below may be administered with the intent to treat the participant's malignancy.

Treatment regimen is described in Table 1.

Table 1 Treatment Regimen.

Regimen Description					
Agent	Premedication; Precautions	Dose	Route*	Schedule	Cycle Length
Eribulin	No routine premedication required, addition of 4 to 8mg of dexamethasone and/or 8 to 16mg of Zofran allowed for nausea as per institutional standard ⁺	1.4mg/m ²	IV, infuse over 2 to 5 min, may be administered per institutional standard	Day 1 and Day 8	21 days (3 weeks)
Pembrolizumab	Not routinely necessary unless prior infusion reaction. ⁺	200mg	IV infuse over ~ 30 min as per institutional standard, infuse prior to starting eribulin infusion, per institutional standard	Day 1	
* Dose reductions may be made as per Tables 3.1-4.9. Further details about dose reductions can					

be found in Section 6.

+Pre-medications can be administered prior to pembrolizumab. Pre-medications for pembrolizumab and eribulin may be administered per institutional standards.

5.2 Pre-Treatment Criteria

5.2.1 Cycle 1, Day 1

Criteria to treat on Cycle 1 Day 1 (Patient does not need to re-meet full eligibility criteria):

- Absolute neutrophil count $>1500/\text{mcL}$
- Platelets $>100,000/\text{mcL}$
- ALT and AST $<2.5 \times \text{ULN}$ in a participant with no documented liver metastases; ALT and AST $<5.0 \times \text{ULN}$ in a participant with documented liver metastases
- Total bilirubin $<1.5 \times \text{ULN}$ ($2.0 \times \text{ULN}$ in a participant with well documented Gilbert's syndrome)

5.2.2 Cycle 1, Day 8 and Day 8 of subsequent cycles

Criteria to treat on Cycle 1 Day 8 and Day 8 of subsequent cycles:

- Absolute neutrophil count $>1000/\text{mcL}$
- Platelets $>100,000/\text{mcL}$
- ALT and AST $<2.5 \times \text{ULN}$ in a participant with no documented liver metastases; ALT and AST $<5.0 \times \text{ULN}$ in a participant with documented liver metastases
- Total bilirubin $<1.5 \times \text{ULN}$ ($2.0 \times \text{ULN}$ in a participant with well documented Gilbert's syndrome)

5.2.3 Day 1 of subsequent cycles

Criteria to treat on Day 1 of subsequent cycles:

- Absolute neutrophil count $>1000/\text{mcL}$
- Platelets $>100,000/\text{mcL}$
- ALT and AST $<2.5 \times \text{ULN}$ in a participant with no documented liver metastases; ALT and AST $<5.0 \times \text{ULN}$ in a participant with documented liver metastases
- Total bilirubin $<1.5 \times \text{ULN}$ ($2.0 \times \text{ULN}$ in a participant with well documented Gilbert's syndrome)

Any non-hematologic toxicities must return to baseline or to $< \text{Grade } 2$ beginning with Day 1 of each cycle.

If dose is held or missed on Day 1 of a cycle, that cycle will not be considered to start until the day the dose is actually administered to the patient (ie, D1-D8-rest, X-D1-D8-rest, etc.)

5.3 Agent Administration

5.3.1 Eribulin

Eribulin will be administered by trained medical personnel at the investigational site. Treatment compliance will be monitored through documentation of study treatment administration in the participant's medical record.

Please refer to the FDA-approved package insert for eribulin for product information and a comprehensive list of adverse events.

Eribulin will be administered on Days 1 and 8 of each 21-day cycle. Eribulin should be prepared and administered per institutional standard. Institutional standard procedures include BSA calculations, body weight assessments and dose calculations/recalculations.

5.3.2 Pembrolizumab

Pembrolizumab will be administered by trained medical personnel at the investigational site. Treatment compliance will be monitored through documentation of study treatment administration in the participant's medical record.

Pembrolizumab will be administered in the outpatient clinic on Day 1 of each cycle. Pembrolizumab should be prepared and administered as an approximately 30-minute IV infusion per institutional standard, infuse prior to Eribulin

Please refer to the FDA-approved package insert for pembrolizumab for product information and a comprehensive list of adverse events. Pembrolizumab should be prepared and administered per institutional standard. Institutional standard procedures include BSA calculations, body weight assessments and dose calculations/recalculations. Infusion times may be prolonged in participants who experience an infusion reaction as per section 5.9.

Pembrolizumab should be administered prior to eribulin administration. There should be no overlap in timing of the two administrations.

The standard dose of pembrolizumab is 200mg IV.

5.3.3 *Discontinuation of eribulin*

If eribulin is stopped for toxicity, participants are permitted to continue protocol therapy with pembrolizumab alone.

5.3.4 *Discontinuation of pembrolizumab*

If pembrolizumab is stopped for toxicity, participants are permitted to continue protocol therapy with eribulin alone.

5.4 General Concomitant Medication and Supportive Care Guidelines

5.4.1 General Concomitant Medication Guidelines

Pembrolizumab is a human monoclonal antibody and as such is not expected to be metabolized by the cytochrome P450 (CYP) enzymes or other typical drug metabolizing enzymes. Thus, it is not expected to have any effect on the CYP or other drug metabolizing enzymes in terms of inhibition or induction, and is, therefore, not expected to induce this type of PK-based drug interaction. However, with eribulin there is a potential for interaction with other concomitantly administered drugs through the cytochrome P450 system. Concurrent use of all other drugs, over-the-counter medications, or alternative therapies will be reviewed at each visit. The Overall PI should be alerted if the participant is taking any agent known to affect or with the potential to affect selected CYP450 isoenzymes. Appendix C presents guidelines for identifying medications/substances that could potentially interact with the study agent(s).

Medications or vaccinations specifically prohibited in the exclusion criteria are not allowed during the ongoing trial. If there is a clinical indication for one of these or other medications or vaccinations specifically prohibited during the trial, discontinuation from trial therapy may be required. The investigator should discuss any questions regarding this with the overall PI who will communicate with the Merck Clinical team and Eisai Clinical Team. The final decision on any supportive therapy or vaccination rests with the PI and/or the participant's primary physician.

Acceptable Concomitant Medications

All treatments that the investigator considers necessary for a participant's welfare may be administered at the discretion of the investigator in keeping with the community standards of medical care with the exception of those prohibited medications noted below. Concomitant medications will be reviewed as noted in table 7.

Prohibited Concomitant Medications

Participants are prohibited from receiving the following therapies during the Screening and Treatment Phase of this trial:

- Antineoplastic systemic chemotherapy or biological therapy
- Immunotherapy not specified in this protocol
- Chemotherapy not specified in this protocol
- Biologic or targeted agents not specified in this protocol
- Investigational agents other than pembrolizumab and eribulin
- Live vaccines within 28 days prior to the first dose of trial treatment and while participating in the trial. Examples of live vaccines include, but are not limited to, the

- following: Measles, mumps, rubella, varicella/zoster, yellow fever, rabies, BCG, and typhoid vaccine.
- Systemic glucocorticoids for any purpose other than to modulate symptoms from an event of clinical interest of suspected immunologic etiology. The use of physiologic doses of corticosteroids (10 mg prednisone by mouth daily or equivalent) is allowed.
 - Care should be taken with concomitant use of strong CYP3A4 inhibitors/inducers (e.g. ketoconazole and itraconazole; see Appendix C) and eribulin. An alternate medication with no or minimal potential to inhibit CYP3A4 should be considered. If a strong CYP3A4 inhibitor is co-administered with eribulin, participants should be closely monitored for adverse reactions.
 - Participants who, in the assessment by the investigator, require the use of any of the aforementioned treatments for clinical management should be removed from the trial. Participants may receive other medications that the investigator deems to be medically necessary.
 - There are no prohibited therapies during the Post-Treatment Follow-up Phase.

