2.5.2.3 Pharmacokinetics clinical development of Eribulin

In clinical studies, eribulin 's PK is characterized by a rapid distribution phase, with a prolonged elimination phase after intravenous infusion. The disposition of eribulin follows linear kinetics over the dose range studied (0.25mg/m²- 4.0mg/m²). It has low plasma clearance, with a mean clearance=1.16-2.42 L/hr/m², a large mean volume of distribution at steady state (43-114 L/m²) and a half-life of elimination of 40 hours. The human plasma protein binding of eribulin occurs at concentrations of 100ng/mL to 1.000ng/mL and ranges from 49% to 65%. Eribulin exposure after multiple doses is comparable to a single dose, with no accumulation of eribulin with weekly administration. As expected based on work in pre-clinical models, metabolism is a minor component of eribulin clearance. Metabolites represent less than 0.6% of parent compound in plasma. Renal elimination is also a minor route of eribulin excretion, with less than 10% of drug excreted unchanged in urine. Most of excretion of eribulin is fecal and unchanged. It is unknown if eribulin is excreted into human milk.⁶⁴

Eribulin does not induce or inhibit hepatic CYP3A4 activity at clinically relevant concentrations. Concomitant administration of ketoconazole, a CYP3A4 inhibitor, or rifampicin, a CYP3A4 inducer, had no effect on exposure to eribulin. Eribulin does not induce or inhibit CYP1A, CYP2C9, CYP2C19, CYP2D6 activity at clinically relevant concentrations.⁶⁴

Hepatic impairment may decrease the clearance of eribulin and prolong the elimination half-life, resulting in increased exposure to eribulin. As such, it is proposed that the eribulin dose in patients with moderate hepatic impairment should be adjusted. No studies for patients with severe hepatic impairment have been performed.⁶⁴

Moderate renal impairment (CrCL 30-50 mL/min) may also impact the clearance of eribulin, resulting in increased exposure. As such, it is proposed that eribulin dose in patients with moderate renal impairment should be adjusted. No studies for patients with severe renal impairment have been performed.⁶⁴

Population PK analyses based on Phase 1 and 2 studies showed that eribulin meslyate's clearance is affected by body weight, serum albumin, alkaline phosphatase

and bilirubin. The effects of age, gender, race and concomitant medications (CYP3A4 inhibitors and inducers) on clearance were not found to be significant.⁶⁴

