Unchanged eribulin was the major circulating species in plasma following administration of ¹⁴C-eribulin to participants. Metabolite concentrations represented <0.6% of parent compound, confirming that there are no major human metabolites of eribulin.

Cytochrome P450 3A4 (CYP3A4) negligibly metabolizes eribulin *in vitro*.

Excretion

Eribulin is eliminated primarily in feces unchanged. After administration of ¹⁴C-eribulin to participants, approximately 82% of the dose was eliminated in feces and 9% in urine. Unchanged eribulin accounted for approximately 88% and 91% of total eribulin in feces and urine, respectively.

Drug Interaction Studies

Effect of Strong Inhibitors or Inducers of CYP3A4 on Eribulin: The effect of a strong CYP3A4 inhibitor and a P-gp inhibitor, ketoconazole, on the PK of eribulin was studied in a crossover trial of 12 participants with advanced solid tumors. No clinically relevant PK interaction was observed when eribulin was administered with or without ketoconazole (the geometric mean ratio of the AUC: 0.97; 90% CI: 0.83, 1.12).

The effect of a CYP3A4 inducer, rifampin, on the PK of eribulin was studied in a crossover trial of 14 participants with advanced solid tumors. No clinically relevant PK interaction was observed when eribulin was administered with or without rifampin (the geometric mean ratio of the AUC: 1.10; 90 CI%: 0.91, 1.34).

Effect of Eribulin on CYP Substrates: Eribulin shows no induction potential for CYP1A, CYP2B6, CYP2C9, CYP2C19, and CYP3A in primary human hepatocytes. Eribulin inhibits CYP3A4 activity in human liver microsomes, but it is unlikely that eribulin will substantially increase the plasma levels of CYP3A4 substrates. No significant inhibition of CYP1A2, CYP2C9, CYP2C19, CYP2D6, or CYP2E1 was detected with eribulin concentrations up to 5 µM in pooled human liver microsomes. In vitro drug interaction studies indicate that eribulin does not inhibit drugs that are substrates of these enzymes and it is unlikely that eribulin will affect plasma levels of drugs that are substrates of CYP enzymes.

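### Minor: Section 5.4.1 can be read as removing participants whom it says to monitor for a strong CYP3A4 inhibitor; separately, Section 5.6 does not secure the week-12 scan that the primary endpoint needs after early stopping

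*Combined protocol and SAP*

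**What the plan says.** **Concomitant drugs (Section 5.4.1).** The list of prohibited medications opens: "Participants are prohibited from receiving the following therapies during the Screening and Treatment Phase of this trial". One of its bullets begins "Care should be taken with concomitant use of strong CYP3A4 inhibitors/inducers". That bullet asks that an alternative drug be considered and then adds: "If a strong CYP3A4 inhibitor is co-administered with eribulin, participants should be closely monitored for adverse reactions". The bullet after it concerns participants who, in the investigator's judgement, "require the use of any of the aforementioned treatments for clinical management should be removed from the trial". It makes no exception for the CYP3A4 item.

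Earlier in 5.4.1 the tone is softer. The Overall PI is to be told of any CYP-active drug. If a prohibited medication is clinically indicated, "discontinuation from trial therapy may be required". The final decision on supportive therapy is left to the PI and/or the participant's primary physician.

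**Scans and the primary endpoint.**
- Section 11.1 schedules restaging every 6 weeks, within 3 days either way.
- Section 5.1 keeps restaging on schedule when treatment is delayed.
- Section 5.6 covers participants who come off for a reason other than progression. It requests scans where possible, every 8 weeks or 2 months, until progression, death or new systemic therapy.
- Section 13.1 counts as failures, among others, participants who lack a scan at 12 weeks after baseline.

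**The concern.** **(a) Two instructions for one drug.** A participant who needs a strong CYP3A4 inhibitor is to be monitored under one bullet and, on a literal reading, removed under the next. A treating physician who follows the second could end study therapy for a reason that the protocol's pharmacokinetic data do not support. The word used is also removal from the trial, where the earlier paragraph speaks of stopping trial therapy. Those are different acts: a participant who stops therapy can still be scanned and followed.

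**(b) A missing scan scored as a failure.** This does not depend on CYP3A4 drugs. Anyone who stops both agents before week 12 without progression moves from the 6-week schedule to the looser one in 5.6. The plan then does not secure the scan that its endpoint rule requires. A participant who is progression-free at week 12 can be counted as a failure only because no scan was scheduled then. That would pull the observed 12-week rate down for a reason unrelated to disease.

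**Working it through.** **(a) Comparison of the wording, case by case.** No arithmetic applies here.

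- *A therapy plainly banned, such as immunotherapy outside the protocol.* The list prohibits it and the next bullet gives the consequence. There is no conflict.
- *A strong CYP3A4 inhibitor that is required.* The caution bullet foresees co-administration and sets out monitoring. The removal bullet reaches back over the whole list and sets out removal. The two conflict.
- *A strong CYP3A4 inducer that is required.* The caution bullet asks only for care, and its monitoring sentence names inhibitors alone. The conflict with removal remains, but permission with monitoring is not spelled out.

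The protocol's own data on eribulin favour caution:

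- Section 2.5.2.3, population analysis: the effects of "concomitant medications (CYP3A4 inhibitors and inducers) on clearance were not found to be significant".
- Section 8.2.1, ketoconazole, which "was studied in a crossover trial of 12 participants with advanced solid tumors": AUC ratio 0.97 (90% CI 0.83 to 1.12). "No clinically relevant PK interaction was observed when eribulin was administered with or without ketoconazole".
- Section 8.2.1, rifampin, 14 participants: AUC ratio 1.10 (90% CI 0.91 to 1.34), with the same conclusion.

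The crossover studies are small, but all three sources agree. The exclusion criteria in Section 3.2 contain no CYP3A4 item.

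**(b) Timing of the scan after early stopping.** Weeks are counted from the start of treatment for simplicity. Section 5.6 does not say where its interval starts, so that is an assumption in each case.

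- On schedule: scans at weeks 6 and 12. Week 12 is day 84, and the 3-day window runs from day 81 to day 87.
- Last scan at week 6, interval counted from that scan: 6 + 8 = week 14, or day 98. That is 98 − 87 = 11 days after the window closes.
- Stop between weeks 6 and 12, interval counted from stopping: between 6 + 8 = week 14 and 12 + 8 = week 20.
- Stop before week 6 with only the baseline scan (up to 2 weeks before treatment), interval counted from that scan: first scan at weeks 6 to 8, second at weeks 14 to 16. Week 12 falls between them.
- Stop at week 4, interval counted from stopping: 4 + 8 = week 12. The scan is on time.

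The week-12 scan can therefore be missed by someone who follows 5.6 exactly, though not always.

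**Size per participant.** Section 13.2 requires at least 9 progression-free of 19. The exact binomial gives P(X ≥ 9 | n = 19, p = 0.6) = 0.9115, which reproduces the stated 91%. One participant moved from success to failure changes the observed rate in an arm by 1/19 = 5.3 percentage points.

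**The case against.** **On (a).** A specific instruction for a drug class would normally govern over a general removal rule, and the treatments referred back to are most naturally the ones actually banned. The list also mixes bans with notes: its last bullet concerns the follow-up phase, and the glucocorticoid bullet allows physiologic doses. Bullet position is therefore weak evidence of a prohibition, and bullet levels may differ in the original file. Section 5.4.1 gives a route to the PI. Appendix C, to which the caution refers, could not be checked. All of this stands as evidence of intent, and it keeps the point minor. It does not reconcile the two bullets. The investigator's judgement bears on whether the drug is required, not on what follows once it is.

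A reader might infer that the plan enrols people on these drugs and then removes them. The documents do not support that sequence. The list covers screening as well as treatment, so if the item were a ban it would already apply at screening; if it is not a ban, nobody is removed.

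**On (b).** Counting a missing assessment as a failure is a conservative rule. It can only lower the number of successes, so it cannot inflate the type I error. A participant who stops one agent for toxicity may continue the other under 5.3.3 and 5.3.4, and so stays on the regular schedule. A clean scan at week 14 would also show that the participant had not progressed by week 12. These points stand and limit the size. However, 13.1 as written makes no provision for a later clean scan, and a conservative rule is not a reason to leave the required scan unscheduled.

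**Conclusion.** Both parts hold, and both are minor.

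(a) is a drafting fault. The text conflicts for a required strong inhibitor. For inducers the caution asks only for care, so the permissive side is weaker. The likely intent is caution.

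(b) has more bearing on the primary endpoint. Following the plan as written can score a progression-free early stopper as a failure, at 5.3 points of an arm's observed rate for each one. The week-14 example assumes that the interval in 5.6 runs from the last scan.

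A reader might infer a loss of power. With one participant per arm certain to be counted as a failure and the others at a true rate of 60%, P(X ≥ 9 | n = 18) = 0.8653; with two, P(X ≥ 9 | n = 17) = 0.8011. The arithmetic is right, but the documents give no frequency for early stopping without progression, for a missing week-12 scan, or for need of a strong CYP3A4 drug. No expected power loss can be claimed. Nor do the documents tie these figures to the CYP3A4 wording: that would require a drug with no alternative, literal removal despite the PI's discretion, timing before week 12, no progression, and no qualifying scan.

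**What to change.** 1. In 5.4.1, move the CYP3A4 caution to a separate paragraph on drugs to be used with care, or limit the removal sentence to the therapies that are actually prohibited.
2. Word that sentence as discontinuation of protocol therapy, to match the earlier paragraph of 5.4.1, so that follow-up and scans continue.
3. In 5.6, state that participants who stop therapy before week 12 without progression keep the scheduled week-12 scan, with the 3-day window of 11.1. State also whether new systemic therapy before week 12 ends that requirement, since 5.6 now stops scans at that point.

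Items 1 and 2 cost a wording amendment. Item 3 costs an occasional retimed or additional off-treatment scan. Its practical benefit depends on how many participants have still to reach week 12. The protocol notes that long-term follow-up is ending but does not say whether treatment continues. If all participants are past week 12, the useful remaining step is to report, by arm, how many failures rest only on a missing scan.
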